3.0: Study Design

3.1: Overview

This matched cohort study will compare adverse outcomes in women vaccinated in pregnancy to unvaccinated pregnant women. The primary analysis will draw the unvaccinated pregnant women from the pre-pandemic period, with supplementary analyses conducted with controls from the pandemic vaccination period. The matching process is detailed in section 3.6.

3.2: Study population

Pregnant women will be identified for inclusion in the matched cohort study through the COPS study database¹. The COPS study database includes all women aged 11 to 55 at the time of conception who were known to be pregnant in Scotland from 01 January 2015 to the present date. In the COPS database, pregnancies are followed-up from conception to the end of the puerperium (six weeks after end of pregnancy) for women and the end of the neonatal period (28 days following birth) for live born babies.

3.3: Study period

The matched cohort study will cover the time period 01 January 2015 to the date of data extraction for the analyses. There are three study periods referred to in this protocol, as follows:

- Pre-pandemic period (01 January 2015 to 29 February 2020)
- Pandemic pre-vaccination period (from 01 March 2020 to 07 December 2020; not included in the analyses described in this protocol)
- Pandemic vaccination period (from 08 December 2020 to date of data extraction)

Vaccinated individuals will have received any COVID-19 vaccine in the six weeks preceding conception or at any point between conception and the end of pregnancy between 08 December 2020 to the date of data extraction, and unvaccinated individuals will be identified from the pre-pandemic period (primary analysis) and the pandemic vaccination period (supplementary analyses 1 & 2).

3.4: Data Sources

This study will involve linkage and analysis of routinely collected electronic health records on maternal, pregnancy and neonatal outcomes, vaccination data and other covariates of interest.

¹ Stock SJ, McAllister D, Vasileiou E, *et al.* COVID-19 in Pregnancy in Scotland (COPS): protocol for an observational study using linked Scottish national data. *BMJ Open* 2020;**10**:e042813. doi: 10.1136/bmjopen-2020-042813. Available from: [COVID-19 in Pregnancy in Scotland \(COPS\): protocol for an observational study using linked Scottish national data | BMJ Open](#)

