Pregnant women will be identified through the COPS² study database if they appear on one or more of the data sources listed for the identification of pregnant women in Table 1.

Table 1: Overview of data sources used for analysis

Data	Data source

Datasets required to identify pregnant women in the general population and associated pregnancy start and end dates:
	
 • New national data return developed as part of the response to the COVID-19 pandemic providing information on women booking for antenatal care with NHS maternity services: for identification of women with ongoing pregnancies in near real-time (all other records that identify end of pregnancy events) • GP consultation data: for identification of women with early miscarriage or ectopic pregnancy not managed in hospitals • Scottish Morbidity Record (SMR) 01: for identification of women with early miscarriage or ectopic pregnancy managed in hospitals • Termination of pregnancy statutory notifications (AAS records) • SMR 02: for identification of later miscarriage, stillbirth, and live births managed in hospital (and some home births) • National Records of Scotland (NRS) statutory stillbirth registrations • National Records of Scotland (NRS) statutory live birth registrations • New national data return developed as part of the response to the COVID-19 pandemic providing information on live births notified by maternity services to NHS Board child health administrative departments: for near real-time access to data that allows intergenerational linkage of records relating to mothers and their babies. 
Note that this is already established as part of the COPS study and methodology is set out in the Protocol for estimating the number of COVID-19 vaccinations delivered to pregnant women in Scotland and for describing the uptake and coverage of vaccination in the pregnant population.

Datasets required to identify characteristics of pregnant population
	
 • Covariates of interest include: Maternal age, deprivation score, urban/rurality score, ethnicity, pre-pregnancy clinical vulnerability exc diabetes, diabetes, BMI, smoking status, and linked PCR test data to capture confirmed cases of COVID-19 infection. 
Note that all are available through the COPS study database.

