Maternal pre-pregnancy clinical vulnerability (excluding diabetes)	Clinically extremely vulnerable (on shielding list)	
	Clinically vulnerable (Q-COVID comorbidity excluded diabetes or hypertension)	
	Not clinically vulnerable	
Diabetes	Yes – pre-existing diabetes	If we only have a small number of women that are identified as having diabetes but it is unknown as to whether this is gestational or pre-existing, then we will combine gestational diabetes & unknown diabetes groups.
	Yes – gestational diabetes	
	Yes – diabetes onset unknown	
	No diabetes	
BMI at antenatal booking	Underweight (<18.5) Healthy weight (18.5-<25) Overweight (25-<30) Obese (30-<40) or severely obese (≥40) Unknown	Obese and severely obese will be combined.
Smoking at antenatal booking	Yes - current	
	Yes - former	
	No - never	
	Don't know	

Note: categories will be collapsed as required.

We have considered, but are currently not planning to include, several other covariates. These include parity and pregnancy-related complications other than gestational diabetes. Information on parity is only available on delivery records, negating its inclusion for any of the early pregnancy outcomes, and there are concerns about the quality of these data. Theoretically, pregnancy-related complications (e.g. pregnancy-induced hypertension and pregnancy-related bleeding) could be on the causal pathway between vaccination status and other adverse outcomes so will not be included as potential confounders. However, additional analyses will be conducted as appropriate if we see signals of associations between vaccination and outcomes that might be due to differential vaccination uptake in women with pregnancy-related complications. Gestational diabetes was considered as an exception to this and included as a covariate. This is because pregnant women with gestational diabetes were added to the list of individuals clinically vulnerable and therefore eligible for vaccination in priority risk group 6 early in the vaccination programme (March 2021), possibly leading to high uptake in this group, and the known association between diabetes and many of the outcomes under study.

3.6: Cohort study matching

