First, a model with no covariates will be fitted to calculate the unadjusted OR for the association between vaccination status and each outcomes of interest. Subsequently, we will calculate an adjusted OR for the association between vaccination status and each outcomes of interest, by adding all covariates to the model (Table 4). P-values and confidence intervals will be reported for all models. For some rarer outcomes, we will adjust our modelling approach as required (e.g. re-classification of groupings or removing insignificant covariates). Covariate pairs will be assessed for collinearity before adding to the model. For any covariate pairs that are highly correlated, only the covariate which has the biggest impact on the association between the exposure and outcome will be included in the model.

As previously described (section 3.5.2), analyses will be conducted first looking at the association between having any vaccination and outcomes, and then in sub-group analyses stratified by vaccine classes and individual vaccine types;

- Vaccine type: Pfizer, AstraZeneca, Moderna, Janssen
- Vaccine group: Pfizer and Moderna (mRNA); AstraZeneca and Janssen ((adeno)virus vector)
- Number of vaccine doses

Our main analyses will include all pregnancies/births, regardless of whether there is evidence that it was singleton or multiple, with sensitivity analyses conducted restricting to only pregnancies/births where there was no evidence it was a multiple. We often do not know whether pregnancies which end early (e.g. due to miscarriage) were singleton or multiple, hence the decision to only include pregnancies with *no evidence* of being a multiple in these sensitivity analyses.

4.5: Additional analyses

There are two further analyses that may subsequently be conducted to assess the association between vaccination and adverse outcomes, specifically:

1. We will consider using all data from the pre-pandemic period to predict the expected number of outcomes among the vaccinated pregnant women, and compare this predicted number to the observed number within the vaccinated group of women.
2. For rarer outcomes (e.g. for congenital anomalies, microcephaly), we will consider a nested case control study if signals are identified in this present matched cohort analysis but wide confidence intervals due to the small number of events negate any meaningful conclusions. This design maximises power to assess any association between vaccination and these rare outcomes.

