Appendix Table 3: ICD-10 codes for identifying hypertensive disorders of pregnancy

ICD-10	Condition
O11	Pre-eclampsia superimposed on chronic hypertension
O13	Gestational [pregnancy-induced] hypertension
O14.0	Mild to moderate pre-eclampsia
O14.1	Severe pre-eclampsia
O14.2	HELLP syndrome
O14.9	Pre-eclampsia, unspecified
O15.0	Eclampsia in pregnancy
O15.1	Eclampsia in labour
O15.2	Eclampsia in the puerperium
O15.9	Eclampsia, unspecified as to time period
Considered but not included for this category	
O10	Pre-existing hypertension complicating pregnancy, childbirth and the puerperium
O12	Gestational [pregnancy-induced] oedema and proteinuria without hypertension
O16	Unspecified maternal hypertension

SMR01 and SMR02 records with a relevant date of admission and any relevant ICD10 code recorded against main condition or any other condition will be used to identify admissions for the above 3 conditions. All SMR02 record types will be included (i.e. antenatal, delivery, and postpartum admissions).

Appendix 2: Rationale for selection of pregnancy-related outcome measures to be used in COPS study to assess impact of COVID-19 infection and safety of COVID-19 vaccination

A list of outcomes to be examined post-infection was drawn up in May 2020 for the initial COPS protocol document, based on what was known about COVID-19 at that point. A provisional list of outcomes to be examined post-vaccination (as part of vaccine safety monitoring) was drawn up in April 2021, based on a review of the following sources conducted up to 12 Feb 2021.

- MHRA public assessment record for the Pfizer vaccine (released at the time the MHRA first gave approval for use on 2 Dec 2020) - <https://www.gov.uk/government/publications/regulatory-approval-of-pfizer-biontech-vaccine-for-covid-19>
- MHRA public assessment record for the Oxford vaccine (released at the time the MHRA first gave approval for use on 30 Dec 2020) - <https://www.gov.uk/government/publications/regulatory-approval-of-covid-19-vaccine-astrazeneca>. No public assessment records for other vaccine types available at the time of review
- Data from the MHRA on possible adverse events reported through the Yellow Card scheme up to 31 Jan 2021. <https://www.gov.uk/government/publications/coronavirus-covid-19-vaccine-adverse-reactions>

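### Table 4 removes hypertension from the clinical-vulnerability covariate without giving it a covariate of its own, so pre-existing hypertension alone goes unadjusted in every model

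*Protocol*

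**What the plan says.** Three places in the protocol describe the same covariate.

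- Table 1 (section 3.4) lists it as "pre-pregnancy clinical vulnerability exc diabetes".
- The row heading in Table 4 (section 3.5.3) is "Maternal pre-pregnancy clinical vulnerability (excluding diabetes".
- The middle level in that row is "Clinically vulnerable (Q-COVID comorbidity excluded diabetes or hypertension". The top level is "Clinically extremely vulnerable (on shielding list".

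The other Table 4 rows are deprivation, urban-rural status, ethnicity, diabetes, BMI and smoking. Section 4.4 obtains the adjusted odds ratio "by adding all covariates to the model (Table 4". Section 3.6 matches on maternal age and gestational age, plus season of conception for pre-pandemic controls.

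Section 3.5.3 leaves out most complications on the ground that "pregnancy-related complications (e.g. pregnancy-induced hypertension and pregnancy-related bleeding) could be on the causal pathway" between vaccination and other outcomes. Gestational diabetes is kept as an exception because it affected vaccine eligibility and is associated with many of the outcomes.

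Hypertensive disorders of pregnancy are a primary outcome in Table 2. Their code list in Appendix Table 3 includes O11, "Pre-eclampsia superimposed on chronic hypertension". O10, pre-existing hypertension, is listed there as considered but not included.

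Controls for the primary analysis come from the "Pre-pandemic period (01 January 2015 to 29 February 2020") and must have completed outcome-specific follow-up by its last day.

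**The concern.** Diabetes is taken out of the vulnerability covariate and put back as a separate row. Hypertension is taken out and not put back, and neither the row heading nor Table 1 tells the reader so. Chronic hypertension is a precondition of one outcome code (O11), so it bears directly on the risk of a primary outcome.

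The protocol's introduction says vaccine was offered by age and clinical risk group, so chronic conditions may differ in frequency between vaccinated women and controls. If hypertension does, the adjusted odds ratio for hypertensive disorders carries that difference, in the primary analysis and in both supplementary analyses. Appendix 3 reuses the same covariates for the infection analyses, so the gap carries over.

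A second, weaker question concerns the top level. It is defined by a list drawn up because of COVID-19, while the primary controls were pregnant before the period that the protocol calls the pandemic.

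**Working it through.** **1. Is hypertension restored anywhere?**

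- Table 4 rows: no row for hypertension.
- Matching variables: none.
- Clean window: it removes women with an earlier record of the outcome in the same pregnancy. O10 is not an outcome code, so chronic hypertension alone does not trigger it.
- Stated rationale: it concerns hypertension induced by pregnancy as a possible mediator. A condition present before conception cannot be on the pathway from a vaccine given in pregnancy. The only marginal exception is a diagnosis made after a dose in the six weeks before conception.

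The coding as written is then:

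- hypertension only: not clinically vulnerable;
- hypertension and another Q-COVID condition, or on the shielding list: still vulnerable;
- hypertension and diabetes only: not clinically vulnerable, but flagged by the diabetes row.

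**2. Size.** The protocol gives no prevalence of hypertension by vaccination status and no risk ratio for it, so there is no figure to reproduce. Inputs from the protocol: 10% background risk of hypertensive disorders (Table 2), and 5,000 or 10,000 vaccinated women matched 1:3 (section 3.7). Assumed inputs: prevalence p0 of 1-2% in controls, p1 of 1.5-3% in vaccinated women, risk ratio RR of 2, 3 or 5 for hypertension on the outcome, and no true vaccine effect.

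Bias factor for an omitted binary confounder: B = [1 + p1(RR − 1)] / [1 + p0(RR − 1)].

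Example: RR 3, p0 1%, p1 2% gives 1.04/1.02 = 1.020. Largest case: RR 5, p0 1%, p1 3% gives 1.12/1.04 = 1.077.

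The chance of a nominally significant result is 1 − Φ(1.96 − d) + Φ(−1.96 − d), where d = (0.1B − 0.1) / √[0.1B(1 − 0.1B)/n + 0.1 × 0.9/(3n)]. This is unmatched and takes no account of the multiplicity correction.

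| RR | p0 | p1 | B | n = 5,000 | n = 10,000 |
|---|---|---|---|---|---|
| 2 | 1% | 1.5% | 1.005 | 5.1% | 5.2% |
| 2 | 1% | 2% | 1.010 | 5.5% | 5.9% |
| 2 | 1% | 3% | 1.020 | 6.9% | 8.8% |
| 2 | 2% | 3% | 1.010 | 5.5% | 5.9% |
| 3 | 1% | 1.5% | 1.010 | 5.5% | 5.9% |
| 3 | 1% | 2% | 1.020 | 6.8% | 8.7% |
| 3 | 1% | 3% | 1.039 | 12.4% | 20.1% |
| 3 | 2% | 3% | 1.019 | 6.8% | 8.6% |
| 5 | 1% | 1.5% | 1.019 | 6.8% | 8.6% |
| 5 | 1% | 2% | 1.038 | 12.1% | 19.5% |
| 5 | 1% | 3% | 1.077 | 33.4% | 58.2% |
| 5 | 2% | 3% | 1.037 | 11.6% | 18.4% |

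Ten of the twelve cases lie between 1% and 4%. With the imbalance reversed (RR 3, p0 2%, p1 1%) the factor is 1.02/1.04 = 0.981, which would hide harm instead of suggesting it.

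**3. Shielding list.** Primary controls had completed follow-up by 29 February 2020, and the protocol places the start of the pandemic at 1 March 2020. A COVID-19 list cannot have been compiled during those pregnancies. If list membership is used literally, a control's status is either absent or read from a later date. The protocol does not say which, or whether equivalent criteria are applied to older records.

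**The case against.** The strongest reply is that the effect is probably small and every input is assumed. Age is matched, and BMI, diabetes, deprivation and ethnicity are adjusted for; these may absorb part of a hypertension imbalance, so the marginal factors above may overstate what is left. Women with hypertension and another listed condition are still classed as vulnerable. From 16 April 2021 women in any priority group, including adults aged 18-49, could be offered vaccine in pregnancy, so selection by risk group may have been strongest early. Section 5.0 also concedes unmeasured confounding by comorbidities. All of this stands as a limit on size. None of it explains the exclusion, and a general caveat about unmeasured factors does not cover one that linked records could supply.

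On the shielding list, the reply is that Table 1 says all covariates are available in the COPS database, which reaches back to 2015. The label may stand for criteria applied to earlier records, with the rule set out elsewhere. That is fair. A reader might infer that the level exists only among vaccinated women, or that it biases the odds ratio by a stated amount. The documents support neither, because they do not describe the assignment. In addition, supplementary analyses 1 and 2 use pandemic-period controls and avoid this problem, though not the hypertension gap.

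**Conclusion.** The hypertension point holds on the text: the category disagrees with its own heading and with Table 1, no other covariate or matching variable represents hypertension directly, and the stated rationale does not reach a pre-conception condition. The change should be made.

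The size is not known. Under the assumptions above the bias is about 0.5-8%, mostly 1-4%, on a 10% outcome, with nominal false-positive rates of 5.1-33% at 5,000 vaccinated women and 5.2-58% at 10,000. A reader might infer that the study will show a spurious excess of hypertensive disorders, or that hypertension is wholly uncontrolled. Neither follows: the direction depends on an imbalance that the protocol does not report, and related covariates may take up part of it.

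The shielding-list point is secondary and inferential. It justifies a clear definition, not a claim of bias.

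**What to change.** - Make Table 1, the Table 4 heading and the Table 4 category agree on what is excluded.
- Add pre-existing hypertension as a row in Table 4, from diagnoses recorded before conception, with the same sources and the same look-back for vaccinated women and controls. The look-back must be one that the records can support for the earliest control pregnancies. If it is to stay out, give the reason.
- Use O10 only in a sensitivity definition. It is coded during or after pregnancy, so it may follow vaccination, and it is likely to be poorly captured for early losses.
- For the comparison with pre-pandemic controls, define the top vulnerability level by the same record-based, pre-conception criteria in both groups. Keep list membership for the pandemic-control analyses or for a sensitivity analysis.
- Carry the changes into the infection analyses of Appendix 3.

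The cost is the derivation of one flag and the recoding of one covariate, with SMR01 and SMR02 already linked. The drawbacks are some under-recording of hypertension in hospital data and a vulnerability level that differs slightly from list membership, which makes the primary and supplementary adjustment sets less alike unless the record-based version is also run in the latter.

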Outcomes have been aligned as far as possible with the relevant Brighton/GAIA outcome definitions, and also agreed with those in the MHRA / four nations working group on COVID-19 vaccination in pregnancy and comply with those recommended by the WHO³. See Appendix 2 for full rational and sources of information behind included outcomes, definitions, timings etc. as presented in Table 2.

Both primary and secondary outcomes are of interest, with the former being a composite measure including the associated secondary outcomes, and the latter being a narrower measure or subset of the associated primary outcome, e.g. primary outcome = small for gestational age, secondary outcome = very small for gestational age.

Venous thromboembolism in pregnancy is a standard maternal outcome that may be influenced by infection or vaccination and is not the same as vaccine associated thrombosis with thrombocytopenia (VATT), the condition associated with the AstraZeneca vaccine⁴. Similarly, the pregnancy related bleeding outcome includes disseminated intravascular coagulation (DIC) which can occur in association with massive obstetric haemorrhage: again, this is distinct from VATT. Full lists of ICD10 codes used to identify the maternal outcomes venous thromboembolism, pregnancy-related bleeding, and hypertensive disorders of pregnancy are shown in Appendix 1.

³ <https://www.who.int/publications/m/item/safety-surveillance-of-covid-19-vaccines-in-pregnant-and-breastfeeding-women>

⁴ Pavord, S et al (2021). Clinical Features of Vaccine-Induced Immune Thrombocytopenia and Thrombosis. NEJM. DOI: 10.1056/NEJMoa2109908

'Clean windows' will be applied to outcomes, where appropriate, so that only new or incident cases occurring post vaccination will be counted. Specifically, a clean window of the current pregnancy will be applied for the venous thromboembolism, pregnancy-related bleeding, and hypertensive disorders of pregnancy outcomes (i.e. women will only be included if there is no prior record of these outcomes in the current pregnancy). See Table 2. For both congenital anomalies and pregnancy-related bleeding, further descriptive analyses will be conducted looking at more specific diagnoses within these broader outcome groups if we find evidence for an association between vaccination and these outcomes. For example, for pregnancy-related bleeding, we can further disaggregate into early pregnancy bleeding, obstetric haemorrhage, and DIC.

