Longer term child outcomes, including immune function and infection, and neurodevelopment, will be addressed in future work as required.

Other adverse outcomes that are not specific to pregnant women, will be investigated separately for the whole population as part of wider adverse events monitoring in Scotland. If these analyses suggest any signals in the pregnant population, those outcomes would be investigated in the pregnant population using the COPS data infrastructure, as required.

Table 2: Maternal, pregnancy and neonatal outcome measures for monitoring of safety of COVID-19 vaccination in pregnancy

Outcome measure	Definition	Primary or secondary outcome?	Clean window requirement to identify incident cases	Timing of vaccination to be included	Post vaccination risk period to be examined	Estimated background risk of outcome (%)
Maternal outcomes						
Hypertensive disorders of pregnancy	See ICD10 code list. Note that hypertensive disorders can only be diagnosed at >20 weeks.	Primary	No prior record in this pregnancy	Any	Up to E plus PP	10.0
Venous thromboembolism	See ICD10 code list	Primary	No prior record in this pregnancy	Any	Up to E plus PP	0.15
Pregnancy-related bleeding	See ICD10 code list	Primary	No prior record in this pregnancy	Any	Up to E plus PP	30.0 (for postpartum haemorrhage)
ICU admission or death (any cause)	ICU admission as identified on SICSAG record Death from any cause	Primary	None (but exploration to be undertaken of reasons for any pre-vaccination ICU admission where these are documented)	Any	Up to E plus PP	Unknown
Pregnancy outcomes						
Miscarriage	Miscarriage at <24 completed weeks gestation	Primary	None	Up to 23w+6d gestation	Up to 23+6 gestation	10.0 – 20.0

• First trimester miscarriage	Miscarriage at <14 completed weeks gestation	Secondary	None	Up to 13+6 gestation	Up to 13+6 gestation	Unknown
• Second trimester miscarriage	Miscarriage at 14-<24 completed weeks gestation	Secondary	None	Up to 23+6 gestation	14+0 to 23+6 gestation	Unknown
Ectopic pregnancy	Ectopic pregnancy ending at any gestation	Primary	None	Up to 2+6 gestation	Up to E	1.0
Stillbirth	Spontaneous fetal loss at ≥24 completed weeks gestation Any cause of fetal death Losses related to termination of pregnancy excluded	Primary	None	Any	24+0 to E	0.4
Baby outcomes (live births only unless otherwise stated)						

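### Pregnancy complications recorded before the index date are left uncontrolled on a mediator argument that cannot apply to them; the resulting bias could run either way.

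*Protocol*

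**What the plan says.** Section 3.5.3 considers pregnancy complications, naming pregnancy-induced hypertension and pregnancy-related bleeding as examples, and leaves them out because they "could be on the causal pathway between vaccination status and other adverse outcomes so will not be included as potential confounders". The argument is not limited to complications that arise after vaccination.

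The same paragraph makes one exception: "Gestational diabetes was considered as an exception to this and included as a covariate". The reason given is early eligibility for vaccination, "possibly leading to high uptake in this group", together with the known link between diabetes and many of the outcomes. For the other complications there is a conditional promise, covering women affected by them: "additional analyses will be conducted as appropriate if we see signals of associations between vaccination and outcomes that might be due to differential vaccination uptake".

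Section 3.5.1 screens earlier events for three maternal outcomes only: "a clean window of the current pregnancy will be applied for the venous thromboembolism, pregnancy-related bleeding, and hypertensive disorders of pregnancy outcomes". In Table 2 the clean-window column requires nothing for the pregnancy and baby outcomes. For miscarriage the row reads "Miscarriage at <24 completed weeks gestation Primary None" and for stillbirth "Losses related to termination of pregnancy excluded Primary None". Preterm birth, SGA, neonatal death and extended perinatal mortality are the same.

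Section 3.6 sets the index date at the date of vaccination. It matches on maternal age, gestational week and, for pre-pandemic controls, season of conception.

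**The concern.** A mediator has to follow the exposure. A threatened miscarriage or hypertensive admission dated before the vaccination date cannot lie on a path from vaccination to outcome. It can affect whether and when a woman is vaccinated, and it predicts the outcome, which is how a confounder behaves. The protocol concedes half of this when it foresees differential uptake in women with complications.

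These events are also measured. Appendix 1 identifies them from dated SMR01 and SMR02 admissions, and the bleeding list includes threatened abortion (O20.0). The clean window needs the same information in both groups. This is therefore not the unmeasured confounding accepted in section 5.0.

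At stake is the comparison for miscarriage, preterm birth, stillbirth, SGA and perinatal death. If complicated pregnancies are under-represented among the vaccinated, a harm is pulled towards the null. If they are over-represented, a harmless vaccine looks harmful.

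**Working it through.** **1. Is there any control elsewhere?** The protocol gives no figure on this point to reproduce, so its provisions are set side by side.

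- Clean window (section 3.5.1, Table 2): applied to VTE, bleeding and hypertensive disorders as outcomes; none for the outcomes at issue.
- Matching (section 3.6, Table 5): age, gestational week, season; no complications.
- Adjustment (section 4.4, Table 4): gestational diabetes, pre-pregnancy vulnerability, BMI, smoking and demographic factors; no other complication.
- Fallback (section 3.5.3): only if a signal is seen, with content not specified.

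A complication before the index date is therefore uncontrolled in the main analyses of these outcomes.

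**2. Size for miscarriage.** All inputs are assumptions, as the documents give none: share of pregnancies with a bleeding record before the index date p = 0.05; miscarriage risk 0.30 with such a record and 0.08 without; uptake u in these women relative to others. Pre-pandemic controls are taken to carry the background share p.

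- Control risk = 0.05 × 0.30 + 0.95 × 0.08 = 0.0910.
- Share with bleeding among the vaccinated: w = p·u / (p·u + 1 − p).
- Vaccinated risk under a null effect = w × 0.30 + (1 − w) × 0.08.

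| u | w | Vaccinated risk | Apparent RR, true 1.0 | Apparent RR, true 1.2 |
|---|---|---|---|---|
| 0.25 | 0.0130 | 0.0829 | 0.91 | 1.09 |
| 0.5 | 0.0256 | 0.0856 | 0.94 | 1.13 |
| 1 | 0.0500 | 0.0910 | 1.00 | 1.20 |
| 1.5 | 0.0732 | 0.0961 | 1.06 | 1.27 |
| 2 | 0.0952 | 0.1010 | 1.11 | 1.33 |

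Varying p from 3% to 8%, the null RR lies between 0.87 and 0.98 for u from 0.25 to 0.75, and between 1.04 and 1.15 for u from 1.5 to 2.

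**3. Effect on detection.** Assume that all 5,000 vaccinated women and 15,000 controls of section 3.7 enter the miscarriage analysis, with an unmatched pooled two-proportion test, two-sided 0.05, and no multiplicity correction. Power = Φ[(|p1 − p2| − 1.96·s0)/s1], where s0 and s1 are the pooled and unpooled standard errors.

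- No confounding (0.1092 v 0.0910): 96%.
- u = 0.5 (0.1028 v 0.0910): difference 0.0118, s0 = 0.00476, s1 = 0.00489, z = 0.50, power 69%.
- u = 0.25 (0.0994 v 0.0910): 43%.
- At 10,000 v 30,000 with u = 0.5: 93%.

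**4. A second outcome, preterm birth.** Table 2 gives a background risk of 7%. With prevalence c of earlier complications in controls, relative risk R for the outcome, and prevalence ratio r (vaccinated to controls), the bias factor is (1 + r·c·(R − 1)) / (1 + c·(R − 1)). Assume c = 5% and R = 3:

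- r = 0.5: 1.05/1.10 = 0.955. A true 1.20 appears as 1.15, and power at 5,000 v 15,000 falls from 90% to 67%.
- r = 1.5: 1.15/1.10 = 1.045.
- r = 2: 1.20/1.10 = 1.09.

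At r = 1 there is no bias.

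**The case against.** A reader might infer that women already in difficulty sit mainly among the controls, so that the vaccine looks safer than it is. The documents do not support that.

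- No section gives uptake by complication. The only example, gestational diabetes, points to higher uptake, and the same formula then gives a false harm.
- Primary controls are pre-pandemic women who could not decline vaccination, so they carry roughly the background rate. Imbalance arises only if the vaccinated are selected. A pool of women who declined or deferred is a more direct issue for supplementary analyses 1 and 2.
- Deferral is not refusal. A woman who bleeds at 8 weeks and is vaccinated at 14 enters the vaccinated group carrying her bleed and is matched at the later week. That can reverse the imbalance, and a single uptake ratio does not capture it.

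The scope is also limited. Women vaccinated before conception have no earlier complication in that pregnancy. Table 2 notes that hypertensive disorders are diagnosed only after 20 weeks, so for miscarriage the issue is mainly early bleeding.

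The protocol did consider these covariates, names differential uptake and promises follow-up. Its trigger refers to associations, not only harms, so a spurious protective result could also set it off. That stands, but a harm pulled to near the null would produce no association in either direction.

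A reader might also infer that gestational diabetes diagnosed after the index date is counted as a covariate. The protocol does not say so; it gives no timing rule, and the analysis plan may supply one.

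**Conclusion.** The rationale in section 3.5.3 does not fit complications that precede the index date, and for miscarriage, preterm birth, stillbirth, SGA and perinatal death nothing else in the design controls for them. This is confounding of unknown direction, confined to index dates within pregnancy. On the assumed central inputs it moves a null miscarriage RR to between 0.91 and 1.11 as relative uptake runs from one quarter to twice that of other women. A true 1.2 is weakened but not necessarily hidden: at half uptake it shows as 1.13. These sizes rest wholly on assumed prevalence, risk and uptake; the point about timing does not depend on them. Because the fallback depends on a signal, it is a weak safeguard against a masked harm.

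**What to change.** 1. In section 3.5.3, limit the causal-pathway argument to complications first recorded after the index date.
2. For miscarriage, preterm birth, stillbirth, SGA and perinatal or neonatal death, in the primary and both supplementary analyses, derive the existing clean-window flag (any Appendix 1 bleeding, hypertensive or VTE record in this pregnancy before the index date) for vaccinated women and controls. Use it as a baseline covariate, or as an exclusion in a pre-specified sensitivity analysis that runs whether or not a signal is seen.
3. Report the flag's prevalence by group, so that the direction of any imbalance is visible.
4. As a secondary point, state that gestational diabetes is adjusted for only where recorded before the index date, or test this in a sensitivity analysis where dates are poor.

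The cost is protocol wording and one derived variable from records already used for the clean windows, with a small loss of numbers if the flag is used as an exclusion.
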